5.1 Description

The NeuroStar TMS Therapy[®] System is a computerized electromechanical instrument that produces and delivers brief duration, rapidly alternating (pulsed) magnetic fields to induce electrical currents in localized regions of the cerebral cortex. It is a non-invasive tool used for the treatment of Participants with MDD who have not achieved sufficient clinical benefit from antidepressant pharmacotherapy. The NeuroStar TMS Therapy System has been FDA-cleared for use in adults. NeuroStar XPLOR[®] is a clinical research option for the NeuroStar TMS Therapy System that provides features necessary to conduct randomized controlled trials and other TMS research. The active treatment modality is essentially the same for both the NeuroStar TMS Therapy System and NeuroStar XPLOR.

The NeuroStar XPLOR TMS System consists of the following equipment and software:

- Mobile Console (includes processor module, power module, mast, gantry, halo, and display arm)
- System Software; the XPLOR option also includes a dedicated system software application (software version 1.7.5 or greater) with its own dedicated database of participant treatment history, TMS TrakStar[®] application, and TrakStar database that operates only with the corresponding XPLOR Software, maintaining isolation, security, and data integrity of the research.
- TMS TrakStar[®] Data Management System software
- Therapy Coils included with the XPLOR option is a set of three TMS coils:
 - a blinded sham or placebo coil; the sham coil is acoustically matched to protect the integrity of the blind,
 - a blinded active coil, and
 - a standard treatment coil that can be used for performing motor threshold level determination or open-label treatment.
- Head Support System (includes laser positioning aid and coil positioning guide)
- Treatment Chair
- Positioning Cushions (to enhance comfort and positioning of the participant in the required posture for the duration of the treatment session)

The NeuroStar TMS Therapy System also requires supplies and disposables for each treatment session:

- Head Cushion Liner
- Head Side Pad Liner
- Head Positioning Straps
- Earplugs
- SenStar[®] Treatment Link (a single-use medical device)
- Used SenStar Treatment Link Return box

5.2 Method for Assigning Participants to Treatment Groups

Each participant will be assigned a unique identification upon signing the informed consent and assent form. This number will consist of an assigned 3-digit identifier. Participants will be identified by their assigned number and initials on the CRFs and source documents. The PI/Study Sponsor will maintain a master list linking Participant names and the identifying information indicated above

A Phase I randomization schedule will be generated by [name] (Study biostatistician). Participants will not be randomized until all entry (inclusion and exclusion) criteria have been met and all pre-study procedures have been satisfactorily completed. After stratification based on ICF biomarker status, eligible participants will be randomly assigned to receive one of the two treatment regimens (1 Hz or 10 Hz rTMS), and the next available randomization number for the participant's stratum will be recorded in the screening log and on the participant's CRF. Randomization numbers may not be reassigned. A permuted-block procedure will be used to randomly assign the treatment conditions, with a fixed block size for each stratum. Phase II is a trial of cTBS or iTBS for Phase I participants who did not have an adequate clinical response in Phase I. Participants will be assigned to 2 weeks of cTBS if their intracortical facilitation measure is >1.5 (building on the current speculation that cTBS would be expected to decrease cortical excitability and ICF measures). Participants will be assigned to 2 weeks of iTBS if their ICF (baseline assessment for TBS extension trial) is ≤ 1.5 .

Collection of ICF and TMS neurophysiology measures: TMS data will be collected with standard procedures published previously.⁶⁵ Participants are seated in a comfortable chair during the procedure. All participants and research team members wear ear plugs during testing sessions. Surface electromyography (EMG) readings are recorded from the abductor pollicis brevis (APB) muscle. The research team will ensure participants maintain relaxation during the procedures with audio feedback tests. TMS stimulation will be applied to the hand area of the contralateral cortex with a figure-of-eight magnetic coil (with a coil diameter of 70 mm on each loop) using the Magstim 200 magnetic stimulator device. The TMS coil is held tangentially on the head with the handle backward at 45 degrees laterally from the midline to determine resting motor threshold. The optimal coil position is located by moving the coil in 1-cm increments over the motor cortex. The resting motor threshold (RMT) is defined as the stimulation intensity which elicits a motor evoked potential (MEP) of > 50 microvolts in 5 of 10 trials with a relaxed APB muscle. For ICF measurements, a subthreshold conditioning stimulus (CS) which is set to 80% of RMT precedes a suprathreshold test stimulus (TS), which is calibrated to produce an average MEP of 0.5 to 1.5 millivolt peak-to-peak amplitude in the contralateral APB muscle. Conditioning stimuli are delivered to the motor cortex prior to the TS in one of five random interstimulus intervals (ISIs): 2 msec, 4 msec for ICI; 10 msec, 15 msec, and 20 msec for ICF. Changes in TS MEP amplitude of each ISI are expressed as a percentage of the mean unconditioned MEP amplitude. Administration of tests is counterbalanced to prevent order effects. Please see Section 16, Appendix B for detailed methodology for collection of ICF and TMS neurophysiology measures.

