Hence for the present protocol we have designed an effectiveness and target validation trial of 1 Hz vs. 10 Hz rTMS. While the inclusion of a sham arm would be ideal, there are substantial pragmatic and financial barriers to completing such a study as a single site while concurrently addressing other critical National Institute of Mental Health (NIMH) priorities. Studies of 1 Hz rTMS and mechanistic studies of rTMS in adolescents would address a substantial knowledge gap and could provide further innovations. Unfortunately, there is a low probability that this will be studied systematically outside of a federally funded grant and even less likely that the neurobiologic mechanisms associated with 1 Hz and 10 Hz rTMS in adolescent depression will be adequately studied.

Developmentally informed, targeted interventions with rTMS for adolescent depression could reap important gains on an individual and population level as cortical, GABAergic and glutamatergic tone continues to change throughout development setting the stage for important future functions.^{17,53} Prior rTMS research focused on depression often has a fatal flaw as heterogeneous groups of patients have been studied with insufficient clinical characterization.^{33,52} Anhedonia⁵⁴ and adversity^{55,56} in depressed adolescents are important dimensional traits to quantify in terms of GABAergic tone, glutamatergic tone, and treatment responsivity to 1 Hz and 10 Hz rTMS. Examining a cohort of depressed adolescents and healthy controls with TMS neurophysiology would deepen our understanding of the role of GABA and glutamate in the negative valence systems domain.^{56,57}

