Please note that [name] works with a team of Board Certified Child and Adolescent Psychiatrists with expertise in adolescent depression, suicidality, severe psychiatric disorders in childhood, rTMS protocols, and clinical research. These psychiatrists are co-investigators and colleagues. One of these physicians (in the event [name] is away) or [name] is present in the treatment suite during rTMS delivery and available 24 hours a day in the event of emergencies. While our group has never had a participant with emergent mania in an rTMS protocol, we have experience and comfort in addressing psychiatric emergencies in general. We have standard operating procedures that the team of psychiatrists are comfortable with and have experience implementing. For example, this team collectively has had experience in hospitalizing research participants. The overriding guiding principal for our research team is that participant safety is our central priority. Any decisions regarding clinical monitoring, referral for higher levels of treatment, and ongoing study participation are informed by what will optimize each participant's safety and clinical status. Beyond this, the Mayo Clinic Division of Child and Adolescent Psychiatry (11 board certified child and adolescent psychiatrists) always has an individual on call for psychiatric emergencies. While these colleagues are not co-investigators, they receive training on a regular basis regarding ongoing adolescent research efforts. All members of the Child and Adolescent Psychiatry Division have proficiency and comfort in dealing with psychiatric emergencies. They contact the PI ([name]) or the covering research child and adolescent psychiatrist with any emergency involving a research participant. Research participants are ultimately offered standard of care interventions based on clinical presentation and need regardless of stage of participation (to include emergent evaluation in outpatient clinic, emergency medicine visits, or psychiatric hospitalization in Mayo Clinic, Generose 1-West, an 18 bed inpatient unit which is located directly below our neurostimulation treatment suite).

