2.1 Primary Objective

Aim 1 examines the relative efficacy of 6 weeks low frequency (1 Hz) or high frequency (10 Hz) left prefrontal rTMS according to a baseline ICF (**ICF-15 % MEP amp**) measure of glutamatergic tone in depressed adolescents. We will employ a biomarker stratified design. Depressed adolescents will be stratified by baseline ICF low (≤ 1.5) or ICF high (>1.5) groups prior to randomization.

- We expect that 6 weeks of 1 Hz rTMS will have greater efficacy (assessed by improvement in CDRS-R) in depressed adolescents with high baseline ICF compared to adolescents with low baseline ICF.
- We expect that 6 weeks of 10 Hz rTMS will have greater efficacy (assessed by improvement in CDRS-R) in depressed adolescents with low baseline ICF compared to adolescents with high baseline ICF.
- 6 weeks of 1 Hz rTMS will have greater efficacy (assessed by improvement in CDRS-R) than 6 weeks of 10 Hz rTMS in depressed adolescents with high baseline ICF.
- 6 weeks of 10 Hz rTMS will have greater efficacy (assessed by improvement in CDRS-R) than 6 weeks of 1 Hz rTMS in adolescents with low baseline ICF.

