5.5 Blinding of Study

In both phases of the study (phase I and phase II) participants and study team members completing clinical rating scales (Drs. [name], [name], or other designated and trained clinical raters) will be blinded to treatment assignment. The study team member completing clinical rating scales will not be allowed in the treatment suite during therapeutic rTMS sessions (10 Hz, 1 Hz, iTBS, or cTBS). We will recruit adolescent participants with no prior TMS exposure or experience and maintain blind to rTMS treatment assignment (1 Hz or 10 Hz for phase I and cTBS or iTBS for phase II). A pre-post treatment expectancy and experience form will ask that participants and parents guess which treatment (1 Hz, 10 Hz, iTBS, or cTBS) was received.⁸⁸

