7.1 Sample Size Determination

Sample Size Estimation and Power Analysis for the Primary Aim of the Study

Using a putative estimate of effect size ($d \sim 0.61$) as it relates to the Primary Aim, an *a priori* sample size estimation and power analysis was performed for the repeated measures design in the proposed study. The results suggest that a sample size of 25 participants per group ($N=120$) achieves 80% power, at a 0.05 alpha level (two-tailed), to detect standardized group mean differences (Cohen's d) as small as 0.61 in a 2-treatment by 2-biomarker status between-Participants group design with 6 (within-Participants) repeated measurements of the primary outcome (depression severity) having a compound symmetry covariance structure, when the assumed within-Participant correlation between observations (depression severity) on the same Participant is ≤ 0.50 (0.50 was based on guidance from our preliminary rTMS work). We anticipate some dropouts (~20% based on treatment discontinuation results from our previous rTMS studies). Thus, ~120 participants will be enrolled to allow for this expected rate of attrition with the intent of capturing a range of evaluable data for 100 participants. The Power Analysis and Sample Size (PASS) 2016 software, version 14.0.7, was used to carry out the sample size and power analysis.⁸⁹

We recognize that to definitively evaluate the relationship between rTMS Treatment (low frequency 1 Hz rTMS vs. high frequency 10 Hz rTMS) by biomarker status (high baseline ICF vs. low baseline ICF) on depression severity—since this relationship has not been previously studied, we have no previous findings to guide effect size selection for the present effort, and the current study would be the first of its kind to examine this effect in depressed youth—we will possibly need a larger sample size than the 100 participants put forth in this proposal. The selection of 100 participants was, in part, resource-driven. The sample size is designed, in part, to detect a moderate effect and to establish a *proof of concept* so as to expand to a subsequent, larger-scale multi-center study. Nevertheless, the current proposal will permit an evaluation of whether receiving low frequency (1 Hz) rTMS vs. high frequency (10 Hz) rTMS treatment according to patients' baseline biomarker status (ICF) shows initial evidence of a relationship with improvement in depression severity in a depressed adolescent population.

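### Fixed block sizes within each ICF stratum, with no allocation concealment described, could let staff who know past assignments predict some of the next ones

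*Combined protocol and SAP*

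**What the plan says.** Section 5.2 has the study biostatistician generate the Phase I schedule. After ICF stratification, "eligible participants will be randomly assigned to receive one of the two treatment regimens", 1 Hz or 10 Hz, and the next number in the participant's stratum is entered in the screening log and on the CRF. The method is: "A permuted-block procedure will be used to randomly assign the treatment conditions, with a fixed block size for each stratum". The section requires entry criteria and pre-study procedures to be complete before randomisation, and it forbids reuse of randomisation numbers. It does not state the block size, who holds the schedule, how an assignment is released, or whether the size is withheld from the site.

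There are two strata (Section 2.1): "Depressed adolescents will be stratified by baseline ICF low (≤ 1.5) or ICF high (>1.5) groups prior to randomization". Section 1.1 explains the lack of a sham arm by barriers to "completing such a study as a single site".

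Section 5.5 limits blinding to "participants and study team members completing clinical rating scales", and it keeps raters out of the suite during sessions. Section 5.3 puts at least one team member in the room at every session. Section 1.5.2 says that a study psychiatrist, who is the lead or a co-investigator, "is present in the treatment suite during rTMS delivery and available 24 hours a day in the event of emergencies". The same section places that psychiatrist in a room next to the treatment room.

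**The concern.** Permuted blocks of constant length become predictable towards the end of each block. At one site with two strata, one team accumulates both sequences. The arms are easy to tell apart for anyone present: 1 Hz runs without a break, while 10 Hz comes in 4-second trains with 36-second pauses (Section 5.3). Treatment details also reach other staff. Two people complete a pre-treatment checklist in week 1 (Section 6.3), and a daily treatment summary goes into each participant's source document (Section 9.4).

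There is room for foreknowledge to act, even unconsciously. Eligibility includes investigator judgement on suicide risk (Section 4.2). Up to 7 days may pass between screening and baseline (notes to Table 3). ICF is read before randomisation (Section 6.2) and depends on coil placement and on averages of about 10 trials (Section 5.2, Appendix B). A reading near 1.5 decides which of the two sequences supplies the assignment.

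At stake is the comparability of the arms within strata. The primary analysis tests the treatment-by-ICF interaction (Section 7.2), and the hypotheses favour 1 Hz in the high stratum and 10 Hz in the low stratum. Blinded rating protects the measurement of CDRS-R. It does not protect the choice of who enters which cell.

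**Working it through.** **Inputs.** There are two arms and two strata (Sections 5.2 and 2.1). The documents plan 120 participants (Section 3.1) and expect an even ICF split (Section 5.3), so about 60 per stratum. A 1:1 ratio is not stated in words. It is inferred from the equal cells in Section 7.1: "The results suggest that a sample size of 25 participants per group". The block size is not given, so sizes 2 to 12 are shown as an assumption. The documents give no predictability figure to reproduce.

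**Observer assumed.** Someone who knows the fixed size, the stratum, and every earlier assignment in that stratum.

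**Certain assignments.** In a block of 2m with m per arm (A and B), an assignment is forced once the other arm is used up. Each of the m B's is equally likely to fall in any of the m+1 gaps around the A's, so the expected number of B's after the last A is m/(m+1). The same holds for A's after the last B. The expected number of forced positions is 2m/(m+1), and the share is that divided by 2m, which is 1/(m+1).

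Check for blocks of 4: the six orders AABB, ABAB, ABBA, BBAA, BABA and BAAB have 2, 1, 1, 2, 1 and 1 forced positions. That is 8 of 24, or 1/3. Full enumeration agrees at every size shown.

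**Best guess.** Always guessing the arm with more places left in the block gives a success rate of [m + (4^m/C(2m,m) − 1)/2]/(2m). For m = 2: [2 + (16/6 − 1)/2]/4 = 2.833/4 = 70.8%. Chance is 50%.

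| Block size | Certain | Expected number of 120 | Best-guess success |
|---|---|---|---|
| 2 | 50.0% | 60 | 75.0% |
| 4 | 33.3% | 40 | 70.8% |
| 6 | 25.0% | 30 | 68.3% |
| 8 | 20.0% | 24 | 66.6% |
| 10 | 16.7% | 20 | 65.3% |
| 12 | 14.3% | about 17 | 64.3% |

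The counts treat every block as complete.

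**Randomly varying sizes.** A stratum of 60 was simulated 4,000 times. The observer knows the set of possible sizes but not their order, and updates after each assignment. Run with fixed sizes, the simulation returns 33.3% for blocks of 4 and 25.0% for blocks of 6, matching the enumeration.

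| Sizes drawn from | Certain | Best-guess success |
|---|---|---|
| {4, 6} | 5.6% | 69.1% |
| {4, 6, 8} | 2.2% | 67.8% |

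Varying the size removes most of the certainty but hardly changes how often a guess is right.

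**The case against.** Several points on the other side stand.

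- A reader might infer that a quarter to a third of assignments will be known. The documents do not support that as fact. Those shares belong to blocks of 6 and 4, and no size is stated. They also need an observer with full knowledge of the stratum's history.
- A reader might infer that investigators watch treatment being given. Section 1.5.2 puts the psychiatrist in an adjacent room, and Section 5.3 requires only a technician in the treatment room as a minimum. Some staff must know the arm, and investigators could plausibly learn it. More than that is not shown.
- A reader might infer that one team treats, enrols and measures ICF. Section 4.3 says only that a lead investigator or a trained team member obtains consent. With names removed, overlap of roles can be neither shown nor excluded.
- The screening log records a randomisation number. Nothing says that it shows the arm or reveals the next one.
- Section 5.2 already places eligibility and stratification before randomisation.
- The stratum is unknown at consent, because ICF is measured at baseline. Foreknowledge could act only between the ICF reading and assignment, or through the reading itself, which is a physiological recording.
- Selection favouring one frequency equally in both strata would cancel in the interaction, although it would distort the simple effects in Hypotheses 1c and 1d. Selection in opposite directions, as the hypotheses run, would not cancel.

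These points limit how often the weakness could bite. They do not supply what is missing: a concealment mechanism, or any statement that the block size is withheld.

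**Conclusion.** The point holds in conditional form. A fixed block size with no described concealment leaves assignments open to prediction by staff who know past assignments in a stratum and know or infer the size. The share known with certainty would be 1/(m+1): 33%, 25% or 20% for blocks of 4, 6 or 8, and 50% to 14% over sizes 2 to 12.

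This assumes 1:1 allocation and one site. Sections 5.6 and 11 keep some multi-site wording, but the rest of the protocol reads as single-site. No effect on an estimate or on type I error has been calculated. A reader might infer that bias has occurred or is likely, but nothing in the documents shows that. The weakness is a credible route to bias that can be closed at very little cost, so the change is worth making.

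**What to change.** In Section 5.2, replace "with a fixed block size for each stratum" with randomly varying block sizes within each ICF stratum. Give the following equal weight in the same paragraph:

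- The statistician holds the block sizes and the schedule. Both are withheld from staff who screen, enrol or measure ICF.
- Each assignment is released only after eligibility and the ICF value are recorded and locked. The section already sets this order, so what it needs is a mechanism to enforce it.
- Where staffing allows, people who deliver treatment or handle treatment records do not enrol participants or measure ICF.

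The cost is a regenerated schedule for participants not yet randomised and a few sentences of text. It needs no extra participants or visits. The downside is slightly looser balance between arms at any interim moment.

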5.3 Preparation and Administration/Implantation of Investigational Device

Administration of TMS treatment will be consistent with procedures outlined in the NeuroStar[®] User Manual and User training documentation.

Motor Threshold Determination Procedure – per NeuroStar User Manual

Participants in phase I (1 Hz vs. 10 Hz) will receive treatment parameters that have been safely and feasibly utilized in adult and adolescent studies. For 1 Hz and 10 Hz (Phase I) sessions, stimulation will occur at 120% magnetic field intensity relative to the participant's resting motor threshold (MT). In phase II (cTBS vs. iTBS) stimulations will occur at 80% of the magnetic field intensity relative to the participant's resting motor threshold.

Treatment

Participants in Phase I will be stratified based on ICF testing (high or low) at baseline. An ICF of >1.5 at baseline is considered “high” and an ICF ≤ 1.5 is considered “low”. Based on our prior work and review of literature, a sample of depressed adolescents will have an even distribution of high and low ICF values. After stratification, adolescents are randomized to either LDLPFC 1 Hz rTMS with 2400 continuous pulses per session at 120% motor threshold or LDLPFC 10 Hz rTMS with 4 seconds on 36 seconds off for 2400 pulses each session at 120% of resting motor threshold. Hence sessions in each treatment arm with two different types of rTMS (1 Hz and 10 Hz) will have identical intensities (120% motor threshold) durations (40 minutes), number of pulses (2400), and treatment location (LDLPFC). Up to 50 nonresponders in Phase I will be offered to the opportunity to enroll in a Phase II. The decision to enroll in Phase II must be made by the subject no more than 30 days after the last day of Taper Week 3. We will deliver therapeutic rTMS sessions with a Neurostar XPLOR system magnetic stimulator. The research team will localize rTMS treatment sites with the Beam F3 method. Prior research demonstrates that this is a valid and reliable method for scalp location of the dorsolateral prefrontal cortex with comparable results to more expensive, time intensive, MRI-guided approaches.⁸⁷ Our prior research demonstrates that the Beam F3 method is a feasible and reliable method for rTMS treatment localization in adolescents.⁶⁹ Efficacy measures (CDRS-R) and TMS biomarkers will be collected at baseline and weekly. The TMS biomarker panel includes ICF, Motor threshold (MT) Short-interval intracortical inhibition (SICI), long-interval intracortical inhibition (LICI), and cortical silent period (CSP).

Participants in Phase II will be assigned to 2 weeks of cTBS if their intracortical facilitation measure (baseline assessment for TBS extension trial) is >1.5 . Participants will be assigned to 2 weeks of iTBS if their ICF (baseline assessment for TBS extension trial) is ≤ 1.5 . Extension trial TBS will be applied to the LDLPFC with the Beam F3 method. Participants receiving cTBS will receive 10 daily (5 sessions per week for two weeks) 120 second trains of uninterrupted TBS for 1800 pulses at 80% motor threshold. Participants receiving iTBS will receive 10 daily (5 sessions per week for two weeks) 2 second trains every 10 seconds for a total of 570 seconds for 1800 pulses at 80% motor threshold. Efficacy measures (CDRS-R) and TMS biomarkers will be collected at baseline, 1 week, and 2 weeks. The TMS biomarker panel includes ICF, Motor

threshold (MT) Short-interval intracortical inhibition (SICI), long-interval intracortical inhibition (LICI), and cortical silent period (CSP).

Safety Precautions for Seizures and Cardiogenic Syncope during Phase I and Phase II TMS sessions.

We will follow our standard lab procedures for screening to minimize the risk of seizures and syncope, monitoring during treatment sessions, and immediately addressing any induced seizures or syncope during TMS sessions.

With regard to the potential for seizures, all patients will be carefully screened for current or historical factors that may increase the risk of seizures (see Exclusion criteria). The Transcranial Magnetic Stimulation Adult Safety Screen (TASS) will be used to specifically query for any potential seizure or syncope risks. Neurologic disease which may increase the risk for seizures is part of the exclusion criteria.^{74,75} Patients undergoing TMS in the proposed study will not be taking medications which could potentially lower their seizure threshold. All TMS sessions will be supervised by a physician located in the treatment suite and all personnel involved will be provided with training in the identification of potential prodromal signs or symptoms of a seizure, particularly the identification of more subtle behavioral events which may herald the occurrence of a frontal lobe seizure, such as changes in level of consciousness or inattention.

All TMS sessions will be conducted in the neurostimulation suite with access (within minutes) to medical facilities and life-support equipment in the event a seizure should occur.

Monitoring for Seizures during TMS sessions.

Seizure monitoring will be by continuous visual observation. This includes visual monitoring for signs of seizures and twitching of muscles, including the abductor pollicis brevis and the first dorsal interosseous muscles of the contralateral hand. The visual observation monitoring will include monitoring for behavioral events such as changes in level of consciousness or inattention. One or more research team members will be in the room with the participant at all times during TMS sessions for visual observation. At a minimum one TMS technician (with specialized onsite and national training on the delivery of TMS, visual monitoring for signs of a seizure, and training in seizure management) will be in the room with the participant at all times during the TMS session with a study physician in the TMS treatment suite.

Seizure Management

The TMS technician and physician investigators have the capability to manage a seizure if it were to occur. The Mayo Clinic Neurostimulation Lab has direct access (within minutes as it is in the same hospital) to emergency medicine services.

In the event of a seizure or syncopal event, the supervising physician will initiate appropriate clinical care as defined within the clinical rTMS practice. The Pediatric Code Team will also be called immediately. Attention must be taken to minimize the risk of aspiration, and when possible guiding the patient into the left lateral decubitus position is desirable. Because seizures

in the context of TMS are brief (typically <60 seconds) and without serious physical sequelae, efforts will be focused on preventing complications of the seizure rather than initiating any specific medication that is not required unless a seizure is prolonged. The Pediatric Code Team is a hospital-based pediatric rapid response team who will arrive within minutes with life-support equipment (oxygen, suction, blood pressure monitor, CPR equipment) and anticonvulsant/antiepileptic medications. The Pediatric Code Team and the supervising TMS study physician will escort the participant to the emergency medicine department upon stabilization (located in the same hospital as the TMS suite). To date, status epilepticus has never been described following rTMS.^{47,74,75} However, in the rare event this occurs, the participant will be treated in the emergency medicine department with access (within minutes) to neurological consultation.

If a seizure occurs during the study, TMS treatment as part of the study will be discontinued. Ongoing monitoring of mood and neurocognitive symptoms per the study protocol will be offered. Any seizure will be reported to the Mayo Clinic IRB, Data and Safety Monitoring Board (DSMB), Neuronetics, and the FDA as required per agreements, regulations, and policies.

